6 STATISTICAL CONSIDERATIONS

6.1 Sample Size

A sample size of 25 patients (completers) per group provides adequate precision for the estimated dosing regimen difference for relative change in SALT score from Baseline at Week 24. Precision of the estimated difference is quantified by the width of the 90% confidence intervals (CI) for the dosing regimen difference.

6.2 Descriptive Statistics and Common Derivations

Continuous endpoints will be summarized using descriptive statistics (i.e., number of subjects with non-missing data, mean, standard deviation [SD], median, minimum and maximum). Categorical endpoints will be presented as frequencies and percentages. Unless otherwise indicated, the percentages will be computed based on the number of patients included in the concerned analysis population.

Summary tables will be presented by dosing regimen and visit, when applicable.

As the SALT score is by nature a measurement of total surface of the scalp without hair, it is important to note that in the context of this SAP, SALT endpoints will follow these definitions:

Absolute change from Baseline = difference in SALT measurements i.e., Baseline SALT score - post-Baseline SALT score

Relative change from Baseline = percent change of the post-Baseline SALT score, where baseline SALT score is the denominator i.e. (absolute change from Baseline / Baseline SALT score) * 100%

For all other endpoints (e.g., patient satisfaction hair coverage, VAS, patient satisfaction hair coverage quality, clinical laboratory, vital signs, etc.), the change and percent change from baseline will be computed as follows:

Change from Baseline = Assessment value at post-Baseline visit X – Baseline value.

Percent change from Baseline = (change from Baseline / Baseline value]) * 100%.

	STATISTICAL ANALYSIS PLAN, Final v1.0
Protocol Number CP543.2003	Sponsor: Concert Pharmaceuticals, Inc.

6.3 Handling of Dropouts or Missing data

See Appendix 3 for handling of completely or partially missing dates for prior and concomitant medications and AEs. Imputed AE onset and end dates/medication start and stop dates will only be used for the determination of the treatment-emergent/concomitant status. That is, they will not be used to compute any study day or duration and will not be presented in the by-patient data listings.

For the SALT endpoints (e.g., absolute and percent changes from baseline as well as achieving at least 50%, 75%, 80%, and 90% reduction and having a SALT score ≤ 10 and ≤ 20, the Last Observation Carried Forward (LOCF) approach will be implemented for missing SALT score data, e.g., if the SALT score in the Week 16 visit window is missing, the next and closest available ontreatment SALT score measurement before the Week 16 visit window will be used for all remaining SALT assessments: Week 16, Week 20 and Week 24. Missing baseline values will not be carried forward. If a SALT assessment is missing between two non-missing SALT assessments visits, the SALT score at that visit will be interpolated using the mean of the closest pre- and post-assessments.

All other missing efficacy data as well as missing safety data will not be imputed.

6.4 Statistical Tests

No formal hypothesis tests will be conducted. Only two-sided confidence intervals (CIs) at the 90% coverage will be presented. Nominal p-values will be provided.

6.5 Multiple Comparisons/Multiplicity

No adjustment for multiple comparisons and multiplicity will be done for this study since no formal inferential testing will be performed.

6.6 Interim Analysis

No interim analysis is planned for this study.

6.7 Multicenter Studies

Patients will be enrolled at approximately 12 sites. To reduce variability, one rater should perform each clinician dependent assessments for an individual patient for the duration of the study. All investigators using the SALT will be trained prior to use. Data from all sites will be pooled in the summaries and figures

	STATISTICAL ANALYSIS PLAN, Final v1.0
Protocol Number CP543.2003	Sponsor: Concert Pharmaceuticals, Inc.

6.8 Adjustments for Covariates

Not applicable.

6.9 Examination of Subgroups

The analysis of the primary and secondary efficacy endpoints will be repeated for the following subgroups (refer to Section 8 for the definition of each alopecia areata subtype):

- Subjects with alopecia areata at Baseline;
- Subjects with alopecia totalis or alopecia universalis at Baseline;
- Subjects with alopecia ophiasis at Baseline

6.10 Software Version

All analyses will be performed using SAS® software version 9.4 or higher.

7 STUDY SUBJECTS

7.1 Disposition of Subjects

Disposition will be summarized by randomized dosing regimen for all patients who provide informed consent. The following disposition information will be summarized (percentages based on the number of subjects randomized within each dosing regimen, with the exception of the screen failure and reasons for discontinuation):

- The number of patients screened;
- The number and percentage of screen failures. For the percentage of screen failures, the denominator will be the number of patients screened.
- The number of patients randomized;
- The number and percentage of patients within the Safety, mITT and PP analysis populations (if applicable);
- The number and percentage of patients who completed the study, defined as:
 - o Completing Visit 10 (Week 24) and Visit 11 (Week 28)
 - Completing Visit 10 (Week 24) and enrolling into the open-label extension

	STATISTICAL ANALYSIS PLAN, Final v1.0
Protocol Number CP543.2003	Sponsor: Concert Pharmaceuticals, Inc.

- Completing Visit 10 (Week 24) but did not roll into the open-label extension and did not complete the safety follow up visit.
- The number and percentage of patients who prematurely discontinued, and the frequency
 and percentage of each discontinuation reason. The denominator for the percentage of each
 discontinuation reason will be the number of patients who discontinued.

A listing of patient's disposition and a listing of patient's randomization information will be provided. A listing of patients included and excluded from each of the analysis population will also be provided. Patient data listings will list date of informed consent, date of first/last treatment, date of end of study/early termination, and reasons for discontinuation.

7.2 Protocol Deviations

An important protocol deviation is defined as a protocol deviation that might significantly affect the completeness, accuracy, and/or reliability of the study data or that might significantly affect a subject's rights, safety, and/or well-being. The frequency and percentage of patients with at least one important protocol deviation will be summarized by deviation category and dosing regimen based on the Safety analysis population. Non-important and important protocol deviations will be summarized by randomized dosing regimen, classification, and category for all randomized patients and listed by patient in a data listing.

A data review will be conducted before database lock by the Medical Monitor and the sponsor to classify protocol deviations as minor or major. Deviations that may alter or confound interpretation of the study efficacy results will be classified as major deviations. Minor and major protocol deviations will be summarized by randomized dosing regimen, classification, and category for all randomized patients and listed by patient in a data listing.

8 DEMOGRAPHIC AND OTHER BASELINE CHARACTERISTICS

Demographics and Baseline characteristics will be collected at the screening visit, between Day - 28 and -1, and will be summarized by dosing regimen with descriptive statistics based on the Safety analysis population. The list of demographics and Baseline characteristics to be summarized include:

- Age (years) calculated relative to date of consent
- Sex
- Race

	STATISTICAL ANALYSIS PLAN, Final v1.0
Protocol Number CP543.2003	Sponsor: Concert Pharmaceuticals, Inc.

- Ethnicity
- Baseline BMI (kg/m²)
- Baseline SALT total score
- Initial alopecia areata subtype at disease onset, defined below
- Time since initial onset of alopecia areata, in years
- Alopecia areata subtype current episode
- Time since onset of alopecia areata current episode, in years
- Current Nail involvement
- Current Eyelash/eyebrow involvement
- Current other facial hair involvement

Time since initial onset of alopecia areata (years) and time since onset of alopecia areata current episode (years) will be computed as follows:

Lowest integer of [(Date of Screening visit – date of initial/current onset) / 365.25]

A by-patient listing of all demographics and other Baseline characteristics will be provided.

The patient's alopecia areata will be classified by the Investigator into one of three categories defined for this study:

- 1) Alopecia areata: patchy type hair loss,
- Alopecia totalis or universalis: complete hair loss on the scalp with or without body hair loss,
- 3) Alopecia ophiasis: band-like hair loss limited to the periphery of the scalp along the back of the hair line in the occipital region and possibly extending over each ear in temporal regions.

The alopecia totalis and alopecia universalis category will be separated into each individual subtype for summaries.

	STATISTICAL ANALYSIS PLAN, Final v1.0
Protocol Number CP543.2003	Sponsor: Concert Pharmaceuticals, Inc.

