#### 7.1. Patient Inclusion Criteria

- 1. Patient is willing to participate and is capable of giving informed consent. Note: Consent must be obtained prior to any study-related procedures.
- 2. Male or Female patient between 18 and 65 years of age, inclusive, at the time of informed consent.
- 3. Clinical presentation compatible with alopecia areata with a current episode lasting at least 6 months and not exceeding 10 years at the time of Screening. Total disease duration greater than 10 years is permitted.
  - Note: Other causes of hair loss such as cicatricial alopecia (pseudopelade), trichotillomania or syphilis should be ruled out if the clinical presentation is atypical or the history of recurrence and spontaneous remission is unclear.
- 4. Patient has moderate to severe alopecia areata at Screening and Baseline visits as determined by a minimum of 50% scalp hair loss, as defined by a SALT score ≥50.
- 5. Patients involved in any sexual intercourse that could lead to pregnancy:
  - a. Females subjects of childbearing potential must agree to use a highly effective contraceptive method from at least 4 weeks prior to Baseline until at least 4 weeks after the last study product administration.
    - i. Highly effective contraceptive methods include hormonal contraceptives (combined oral contraceptive, patch, vaginal ring, injectable, or implant), intrauterine devices or intrauterine systems, vasectomized partner(s), tubal ligation or bias barrier methods of contraception (e.g. male condom with cervical cap, male condom with diaphragm, and male condom with contraceptive sponge) in conjunction with spermicide.
      - Note: Patients must have been on a stable dose of hormonal contraceptives for at least 4 weeks before Baseline.
      - Note: The above list of contraceptive methods does not apply to patients who are abstinent for at least 4 weeks before Baseline and will continue to be abstinent from penile-vaginal intercourse throughout the study. The reliability of sexual abstinence needs to be evaluated in relation to the duration of the clinical trial and the preferred and usual lifestyle of the patient.
    - ii. Female patient of childbearing potential has had a negative serum pregnancy test at Screening and negative urine pregnancy test at Baseline.
      - Note: A female subject of nonchildbearing potential is defined as follows:

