3 STUDY DESIGN

3.1 Overall Design

This is a randomized, parallel-group, multicenter study to evaluate the efficacy and tolerability of two dosing regimens of CTP-543 (12 mg twice daily [BID] vs 24 mg once daily [QD]) in adult patients with chronic, moderate to severe alopecia areata. Patients will be between 18 and 65 years of age and experiencing an episode of alopecia areata lasting at least 6 months and not exceeding 10 years, with at least 50% hair loss as measured by the Severity of Alopecia Tool (SALT) at Screening and Baseline, and are not concurrently being treated for alopecia areata with other treatments that might affect hair regrowth or immune response. Up to approximately 75% of alopecia areata patients with alopecia totalis or universalis, and no more than 10% of patients with alopecia ophiasis will be enrolled.

A full list of the inclusion and exclusion criteria can be found in Sections 7.1 and 7.2 in the CP543.2003 Protocol.

Patients may be screened up to 28 days prior to initiation of study drug. The Treatment Period is a 24-week dosing period where patients will be randomized to receive either 12 mg BID or 24 mg OD of CTP-543.

[figure not shown]
[figure not shown]

Figure 1: Study Design

Patients will provide informed consent prior to completing any screening procedures. Patients meeting screening criteria will continue to the Day 1 Randomization Visit for review of eligibility and Baseline assessments. Patients meeting all eligibility criteria will be randomized to receive either 12 mg BID CTP-543 or 24 mg QD CTP-543 in a 1:1 ratio. Approximately 60 patients are planned to be randomized in the study (i.e., approximately 30 patients per dosing regimen).

Patients will take the first dose of study drug in the clinic on Day 1 and will be instructed to take study drug every 12 hours. To minimize the bias in the evaluation of study endpoints, patients, investigators, and site personnel will be unaware of the active drug dosing regimen by administering 2 x 12 mg tablets and 2 x placebo tablets 12 hours apart from each other for the 24 mg QD study drug. Patients should dose study drug in the clinic on all Study Visit Days after clinical laboratory blood draws are completed.

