- ⁵ For females of childbearing potential, a serum pregnancy test will be performed at all visits aside from the randomization visit where a urine pregnancy test will be performed.

- 6 If PPD (skin test) is performed, subject will need to return to the clinic 24-48 hours after placement for PPD reading.
- ⁷ Includes hematology and serum chemistry.
- ⁸ When possible, collect pre-dose, except on Visit 11.
- ⁹ Will include thyroid stimulating hormone and hemoglobin A1c at Screening only.
- ¹⁰ Includes total cholesterol, low-density lipoprotein, high-density lipoprotein, and triglycerides.
- ¹¹ Should be performed by the same rater, when possible, for the patient for the duration of the study.
- ¹² For participants who authorize photographs to be taken of their scalp involvement and/or eye and nail involvement.
- ¹³ Will be conducted at Visit 6 (Week 8) only.
- ¹⁴ Collection is ongoing.

	STATISTICAL ANALYSIS PLAN, Final v1.0
Protocol Number CP543.2003	Sponsor: Concert Pharmaceuticals, Inc.

Appendix 2

Output Conventions

TLF will be generated using SAS® and will be displayed on letter size paper with landscape orientation, 1-inch margins, and 9-point Courier New font.

All TLFs will include a header section comprised of the Sponsor's name, the protocol number, the delivery description, the data cut-off date (if applicable), the TLF number, the TLF title, the analysis population, and the page number (Page X of Y). The footer section will include the TLF footnotes, the CRO's name, the date and time of the execution of the program, and the name of the program.

Summary tables and data listings will be summarized by dosing regimen and overall, as appropriate. All data collected per-protocol and all derived variables will be listed.

Mean and median will be displayed to one more decimal place than the original value; SD and CI will be displayed to two more decimal places than the original value; minimum and maximum will keep the same number of decimal places as the original value. If derived parameters are to be summarized, the number of decimals of the derived values is to be chosen on a case-by-case basis, but the rule above applies.

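### SAP Section 8 cuts disease and episode duration to whole years, which on the natural reading lowers each reported mean by about half a year and prints eligible episodes under one year as 0

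*SAP*

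**What the plan says.** SAP Section 8 lists two durations among the baseline characteristics, both labelled in years. It introduces one formula for the pair: "Time since initial onset of alopecia areata (years) and time since onset of alopecia areata current episode (years) will be computed as follows". The formula is "Lowest integer of [(Date of Screening visit – date of initial/current onset) / 365.25", closed by a bracket. The SAP defines no untruncated version of either variable.

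The baseline variables "will be summarized by dosing regimen with descriptive statistics based on the Safety analysis population". SAP Section 6.2 sets out the statistics for continuous variables: "number of subjects with non-missing data, mean, standard deviation [SD], median, minimum and maximum". Under the general display rule in SAP Appendix 2, "Mean and median will be displayed to one more decimal place than the original value", so whole-year values would give means to 0.1 year. Appendix 2 leaves the decimals of derived parameters to be chosen case by case.

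Protocol Section 7.1, criterion 3, requires a current episode "lasting at least 6 months and not exceeding 10 years at the time of Screening". It sets no such cap on the disease as a whole: "Total disease duration greater than 10 years is permitted".

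**The concern.** Taking the integer part differs from rounding. Rounding errors go both ways and roughly cancel in a mean. Truncation takes between 0 and just under 1 year from a patient and never adds any, so the mean is pulled down systematically. Half a year matters little for a variable such as age. It matters more for an episode length that may only run from 0.5 to 10 years.

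The lower end is affected most. A patient must have at least half a year of current hair loss to enter, yet the derived value for anyone in the first year is 0. A table with a minimum of 0 years invites the question whether the entry rule was kept.

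The operator is also not a defined function. Floor is the natural reading, but a programmer could take it as a ceiling, which shifts the mean the other way. What is at stake is how accurately a main descriptor of the population is reported.

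**Working it through.** **Inputs from the documents.** The formula and its two variables (SAP Section 8); the eligible range of 0.5 to 10 years for the current episode, with no 10-year cap on total duration (Protocol Section 7.1); about 30 patients per regimen (SAP Section 3.1: "Approximately 60 patients are planned to be randomized in the study").

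**Assumption.** The documents give no distribution of durations, so several shapes were tried. They state no mean duration either, so there is no figure of the plan's own to reproduce.

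**Step 1: boundary cases, days / 365.25.**
- 183 days = 0.501: floor 0, ceiling 1
- 335 days = 0.917: floor 0, ceiling 1
- 365 days = 0.9993: floor 0, ceiling 1
- 366 days = 1.0021: floor 1, ceiling 2
- 3652 days = 9.9986: floor 9, ceiling 10
- 3653 days = 10.0014: floor 10, ceiling 11

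On the floor reading, every eligible episode up to and including 365 days prints as 0.

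**Step 2: shift in the mean, by hand for the uniform case.** The shift equals minus the mean fractional part. For a uniform spread over 0.5 to 10 years (width 9.5):
- True mean: (0.5 + 10) / 2 = 5.25
- Mean of floor: (0 × 0.5 + 1 + 2 + … + 9) / 9.5 = 45 / 9.5 = 4.74
- Shift: 4.74 − 5.25 = −0.51 year, a fall of 0.51 / 5.25 = 10%
- Share printed as 0: 0.5 / 9.5 = 5.3%

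**Step 3: other shapes, current episode.** Each row is a simulation of 1,000,000 draws kept within 0.5 to 10 years. The scale or median is that of the distribution before truncation. Relative fall = shift / true mean.

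| Assumed shape | True mean | Mean of floor | Shift | Relative fall | Printed as 0 |
|---|---|---|---|---|---|
| Exponential, scale 1 | 1.50 | 0.96 | −0.54 | 36% | 39% |
| Exponential, scale 3 | 3.08 | 2.57 | −0.52 | 17% | 16% |
| Exponential, scale 6 | 4.04 | 3.53 | −0.51 | 13% | 10% |
| Log-normal, median 1, log-SD 0.8 | 1.60 | 1.06 | −0.54 | 34% | 38% |
| Log-normal, median 2, log-SD 0.8 | 2.60 | 2.08 | −0.51 | 20% | 16% |
| Log-normal, median 4, log-SD 0.6 | 4.21 | 3.71 | −0.50 | 12% | 1% |

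The absolute shift stays between 0.50 and 0.54 year throughout. The last two columns do not settle.

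**Step 4: total disease duration.** Uniform over 0.5 to 40 years: 20.25 becomes 19.75, a shift of −0.50 (2.5%). Log-normal with median 8 and log-SD 0.9, floored at 0.5 year: 11.99 becomes 11.48, a shift of −0.50 (4%).

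**Step 5: ceiling reading.** Floor and ceiling differ by exactly 1 for any non-integer value, so the ceiling shift is 1 minus the size of the floor shift: 1 − 0.54 = +0.46 to 1 − 0.50 = +0.50 year. Two programmers reading the line differently would report means one year apart.

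**Step 6: one arm of 30.** With the uniform or the exponential (scale 3) shape, the floor shift in an arm averages −0.51 to −0.52 year (95% range about −0.62 to −0.41). If both arms are drawn from the same distribution, the difference in shift between them averages 0 (95% range about ±0.15 year).

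**The case against.** The strongest reply is that completed years are a common reporting convention and that the SAP states its formula openly. A 6-to-11-month episode does have zero completed years, so a minimum of 0 is compatible with the 6-month rule once the convention is known. That stands: a table showing 0 would not prove a breach of entry criteria. But the SAP labels the variables as time in years, not completed years, and a reader of the table will not have the formula unless a footnote gives it. A footnote would explain the figures without restoring the lost resolution.

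It is also fair that nothing is lost for good. SAP Section 8 promises a by-patient listing of baseline characteristics, and Appendix 2 promises listings of all collected data and derived variables. Exact durations can be recovered wherever full onset dates exist.

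A reader might go further and infer that truncation hides ineligible patients, since a 4-month episode prints as 0 and a 10.9-year episode as 10, and that this feeds into deviations and the per-protocol population. The documents do not support this. Protocol Section 13.6 has the investigator confirm eligibility in source records kept apart from the eCRF. SAP Section 7.2 has the Medical Monitor and the sponsor classify deviations in a data review before lock, and Section 4.2 builds the per-protocol population on that classification. None of these refers to the derived durations.

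Nor does the shift reach a trial result. SAP Section 6.8 gives no covariate adjustment, and the subgroups in Section 6.9 are by disease subtype only.

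**Conclusion.** The point holds as a defect in a descriptive summary. On the floor reading, each mean duration is reported about half a year too low, and every eligible current episode of 6 months to 365 days prints as 0 years. On the ceiling reading, means are about 0.46 to 0.50 year too high. The half-year figure is firm because it barely moves across the shapes tried. The relative fall for the current episode (10% to 36% in the cases shown) and the share printed as 0 (about 1% to 39%) are not firm, because they rest on assumed distributions. For total disease duration the same half year is a smaller fraction of any longer mean.

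The comparison of regimens at baseline is not biased on average, and efficacy, safety and population decisions are untouched. The priority is low; the reason to act is that the correction costs almost nothing.

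**What to change.** In SAP Section 8, replace the whole-year formula for both variables with (Screening date − onset date) / 365.25, reported to one decimal and not truncated. Episodes of 183, 274 and 335 days would then print as 0.5, 0.8 and 0.9 year instead of 0, and the systematic shift would fall to about zero. Naming no integer operator also removes the choice between floor and ceiling.

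Add a sentence on partial onset dates. SAP Appendix 3 imputes dates only for adverse events and medications, and the documents do not say how precisely onset dates are collected. Where only the year is known, the duration is uncertain by up to about a year, so the rule should be stated and the number of patients affected shown.

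The cost is a line or two of SAP text and of code. The one small downside is the need to settle that partial-date rule before database lock.
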